9.1 Inclusion Criteria

To participate in this trial, at the time of screening participants must be:

- Aged 12 to 17 years (confirmed by self-report)
- Located in Australia (confirmed by self-report)
- Experiencing mild to moderately-severe depressive symptoms (as determined by a total score of 5-19 on the self-report Patient Health Questionnaire-9- Adolescent version).
- Own or have access to a smartphone (for receipt of the study interventions)
- Have access to the Internet, an active email address and mobile phone number (for receipt of study activities, invitations, reminders)
- Comfortable with reading English at Year 7-8 level (to ensure comprehension of intervention content)
- Have a parent or guardian who can provide consent for participation.

9.2 Exclusion Criteria

At the time of screening, participants will be excluded if they are:

- Currently experiencing severe suicidal ideation (as determined by a score of ≥ 2 on item 9 of the self-report Patient Health Questionnaire-9-Adolescent version).
- Had serious suicidal ideation in the past month (as determined by self-report).
- A suicide attempt in the past month (as determined by self-report).
- Experiencing nil or severe depressive symptoms (as determined by a score total of ≤ 4 or ≥ 20 on the self-report Patient Health Questionnaire).
- Currently receiving OR about to start (in the next 2 weeks) any psychological treatment for feelings of low mood or depression from a psychologist, psychiatrist or other mental health professional
- Currently taking OR about to start (in the next 2 weeks) any daily prescribed medication (e.g., anti-depressants) for their mental health (low mood, depression or anxiety).

- Unable to gain parental consent to participate (as determined by failure to return parental consent form within their recruitment period).
- Located outside of Australia, not within age range or fail to satisfy any of the other inclusion criteria (as determined by the self-report screener).

9.3 Recruitment Strategy

This study will utilise an online recruitment strategy. Recruitment will take place until the desired sample size is achieved. It is estimated that the sample will be recruited within 8 months, between April to November 2022. All recruitment materials are outlined in Appendix B.

A website for the study will be established and the URL will be included in all study materials. All study adverts will direct participants to the study website, where they will access study information, undertake screening and provide consent.

Study advertisements will be published on the Black Dog Institute website and social media channels including Facebook, Twitter, and Instagram. Study advertisements will also be included in Black Dog Institute internal and external communications, via established professional newsletters to agreed subscribers.

The research team will also contact relevant mental health organisations and services independent of the research team to recruit participants to take part in the study. These organisations will be asked to share the study advertisements on their organisation's communication channels (e.g., website, social media, newsletters, mailing list, in-person clinics) using the same adverts outlined in Appendix B. Support to assist with recruitment will be assumed by the organisation's agreement to post or disseminate recruitment materials. No organisations will know whether a person agrees to participate or not as the recruitment materials will direct potential participants to the study website, which includes further instructions on how to participate, screening, and consent.

The research team will also send two email invitations via electronic direct mailout (sent one month apart) to the Black Dog Institute research database, which consists of individuals who have consented to being contacted about future research studies being conducted by the Institute. The email invitation is included in Appendix B.

The study will also utilise a paid advertising campaign on Twitter, Facebook, Instagram, and Google, for the duration of recruitment. This campaign will use the same adverts outlined in Appendix B.

As the smartphone application utilised in the current study will be released on the Apple and Google Play stores (for approved study participants to use only), a link to the study website will also be included in the description of the app. This will ensure that any young people who discover the application in a store search will be redirected to the study website.

9.4 Screening

Screening will take place via the study website. The homepage of study website will contain a brief version of the PISCF form (see Appendix A) so that participants are aware of key study requirements prior to completing the screening questions. To determine whether a participant is eligible to take part in the study, interested participants will complete a self-report screener

hosted on the study website (see Appendix A for the screening protocol). Participants will be informed that the responses to the screening assessment will be stored for reporting purposes. Consent to undergo the screening procedure will be implied based on individuals' completion of the questions. As this study is targeted at young people, parents or other individuals cannot complete the screening questions on behalf of a youth participant.

Ineligible participants will receive a short thank you message advising them that the study is not the right fit for them at this time. Participants who are ineligible because of severe depressive symptoms or suicidal ideation will be provided with additional information on where to seek help and self-care activities.

9.5 Consent

Once screening is completed, all eligible youth participants will be invited to review the full PICF and provide their personal consent via the online consent form (see Appendix C). Once this is completed, participants will then be invited to register to the study, creating a secure account on the Black Dog Research Engine. To register, participants are asked to provide their full name, email, mobile phone number and age. They are also asked to create a password to ensure account security. Registered participants will then be invited to view the online parental PISCF (Appendix C) to be completed by their parent or guardian. Participants will be asked to complete and submit the online parent consent form within 14 days. After the parental PICF is submitted by the parent, the young person will be automatically notified by the Research Engine of their confirmed involvement in the study and invited to complete the baseline assessment. A copy of the parental PICF will be emailed to the parent's email address provided. A copy of the personal PICF will also be emailed to youth participants via a URL link included in the study welcome email.

Participants will have sufficient time to consider study participation because they have 14 days to complete their parental PICF. Participants will receive three reminders to return their consent form, sent on day 3, day 5, and again on day 10. Participants who fail to complete the parental consent form will be withdrawn from the study.

Once personal and parental consent has been provided, participants will be sent an automated invitation to complete the baseline assessment. The baseline assessment will remain open for a period of 7 days, allowing participants further time to reconsider their consent after its initial provision. Participants can cease the baseline assessment at any time, which will result in their removal from the study.

The consent process used in the current study is appropriate for the study design and data collection method (i.e., online surveys) because participants are being recruited via online methods. Therefore, an online consent procedure aligns with their expectations of research participation. In addition, as this is an internet trial (i.e., all study procedures are conducted online) an online consent form is consistent with the study activities and description. Participants will not be re-consented at each timepoint due to the short duration of the study period and to reduce participant burden.

9.6 Withdrawal of Consent or Participant

Participants will be able to withdraw from the study at any time by the following:

- 1) *Emailing the research team:* By emailing [contact] and providing their full name, date of birth, mobile number with the subject line "withdraw" or equivalent.

- 2) *Via the study withdrawal link provided in the initial study welcome email:* By clicking on the URL at the bottom of the welcome email, participants can withdraw at anytime and actively remove all data from the study without making direct contact with the research team.
- 3) *Failure to complete the baseline assessment within 7 days:* Participants who fail to complete the baseline assessment within 7 days will be automatically withdrawn from the study.

Once withdrawn from the research study, all of participants' personal identifiable data (e.g. name, email address, mobile phone number) will be removed and no further information will be collected from them. The research team will retain some information (e.g. age, gender, symptom severity) for trial reporting purposes. Withdrawn subjects will not be recontacted or followed up. However, to ensure participant safety, withdrawn subjects will be able to report whether their withdrawal from the study was associated with adverse events related or unrelated to the study activities. Participants who actively withdraw will be informed that they can, if they wish, provide feedback about any study activities but there is no obligation to do so.

Failure to complete the primary and secondary endpoint assessments will be considered lost to follow-up for that timepoint but will not withdraw participants from the study. Participants who fail to download or access the study interventions during the study period will not be withdrawn from the study. Withdrawn subjects will not be replaced as the sample size calculations accounts for study attrition.

10. Treatment of Subjects

The study flow is outlined in Appendix K. Upon the provision of full consent, participants will be invited to complete the baseline assessment via an automated email/SMS invitation generated by the Black Dog Institute Research Engine. The outcome measures assessed at baseline are outlined in Appendix D. The baseline assessment is entirely self-report. It will take approximately 20 minutes to complete, and can be completed on any Internet-enabled device. Participants will have 7 days to complete the baseline assessment (from invitation date) and will receive two reminders to complete the assessment (sent on day 3 and day 5). Participants who fail to complete the baseline assessment within 7 days will be withdrawn from the study.

Once baseline is completed, participants will be automatically randomised by the Black Dog Institute Research Engine to one of three trial arms (outlined in Section 10.1). Upon randomisation, participants will be presented with a webpage that provides them with individual instructions and installation advice on the requirements for their trial arm. Participants allocated to Trial Arms 1 and 2 who fail to download the ClearlyMe app within 7 days of randomisation will be sent an email and SMS reminder to download the app.

The study intervention period is 6-weeks, with the primary endpoint assessed at 6-weeks post-baseline. At primary endpoint, participants will be invited to complete the primary endpoint assessment via an automated email/SMS invitation generated by the Black Dog Institute Research Engine. The outcome measures assessed at primary endpoint are outlined in Appendix E. The primary endpoint assessment is entirely self-report. It will take approximately 20 minutes to complete and can be completed on any Internet-enabled device. Participants will have 7 days to complete the primary endpoint assessment (from invitation date) and will receive two reminders to complete the assessment (sent day 3 and day 5). During the intervention

period, the study will also collect data on participants' use of the interventions. This measurement is outlined in Appendix D under 'Intervention Use'.

An additional study assessment will occur at follow-up, with the secondary endpoint assessed at 4-months post-baseline. At secondary endpoint, participants will be invited to complete the primary endpoint assessment via an automated email/SMS invitation generated by the Black Dog Institute Research Engine. The outcome measures assessed at primary endpoint are outlined in Appendix D. The primary endpoint assessment is entirely self-report. It will take approximately 20 minutes to complete and can be completed on any Internet-enabled device. Participants will have 7 days to complete the primary endpoint assessment (from invitation date) and will receive two reminders to complete the assessment (sent day 3 and day 5). Upon completion of the secondary endpoint assessment, trial participation will cease. Participants will be thanked for their time and provided with additional information on mental health and help-seeking resources.

Young people will be reimbursed for the time taken to complete the study assessments. Participants will be reimbursed \$10AUD (electronic gift voucher) for completion of the baseline, post-test and follow-up assessments. The total possible reimbursement will be \$30AUD, which will be emailed and sent via SMS to participants within 14 days of their completion of the scheduled assessment. These amounts are aligned with the best-practice wage-payment model (Dickert & Grady 1999) such that participants are paid for time taken to participate in the study, using the current minimum wage of \$19.84p/hr. In addition, participants allocated to trial arm 2 (guided use of ClearlyMe) will be reimbursed an additional 25AUD (GiftPay Voucher sent by email and SMS) upon randomisation to this group to cover the cost sending and receiving SMSs. This amount was based on the estimated costs of approximately 12 SMS sent per week at \$0.30 per message. Because of this incentive, data integrity checks will be embedded into the online assessments to check for duplicate users at baseline (e.g., emails, and mobile number checks) and to ensure that standards of internet studies are met (Reips, 2002).

All study assessment data will be collected and stored on the Black Dog Institute Research Engine. This Research Engine stores data on secure servers commissioned by the University of New South Wales IT and is hosted on the GovDC Data Centres located in Silverwater, Sydney. The data is stored in a SQL Server 2016 database which is backed up daily on a drive on the server. The drive itself is backed up daily to a tertiary location. Server backups are performed daily and weekly. The daily backups are retained for 2 weeks, the weekly backups for 6 weeks, the monthly backups for 6 months and half yearly backups for 7 years. Access to the servers is strictly controlled and only authorised UNSW IT and Black Dog Institute IT staff can access the servers (VPN) using Two Factor Authentication. UNSW servers are penetration tested regularly for security vulnerabilities and UNSW IT also perform regular security patches and updates on the servers. The Research Engine itself is only accessible to authorised personnel using password protected accounts. For this project, only the Chief Investigator, researchers listed on this application, and the Black Dog Institute IT and data analytics team have access to the research data in the Research Engine. All data will be destroyed 15 years after the completion of the study by the Chief Investigator or Black Dog Institute IT.

The Research Engine automatically generates a unique participant identification code, which is included in all reports. This code enables de-identification of the dataset for analyses. For

analyses, all study assessment data will be exported, via a Microsoft Excel file, from the Research Engine to SPSS Version 26 for analysis by the research team. These files will be stored on UNSW OneDrive and only accessible to the Chief Investigators A and B, Trial Managers, Data Analyst and Senior Research Officer listed on the project. The Trial Manager and Senior Research Officer will de-identify the dataset (i.e., remove name, mobile phone number, email addresses, IP addresses, and free response data) and prepare it (i.e., cleaning and ensuring blinding) for the trial statistician to conduct the primary and secondary analyses. The de-identified and blinded file will then be transferred to the trial statistician for analyses using a password protected OneDrive file. Aggregate deidentified data in a password protected OneDrive file will be retained for future evidence synthesis.

A separate spreadsheet consisting of participants' email addresses and mobile phone numbers alongside their completion of the assessment dates, will also be stored in a password protected file in a private folder on One Drive to enable the GiftPay vouchers to be sent to participants. This file will only be accessible to the Chief Investigators, Trial Managers, Data Analyst and Research Officers/Assistants listed on the project.

As this study is collecting personal information (e.g., mobile phone numbers and email addresses), this information is protected in accordance with the Australian Privacy Act 1988. Participants have the right to access and destroy any personal information collected by this study. If participants have concerns about the way their data has been handled, they are encouraged to notify the Chief Investigator and the UNSW HREC. This information is outlined for participants in the PISCF.

Primary analyses will be conducted to determine the effect of the interventions on depressive symptoms at the primary and secondary endpoints. Analyses will be undertaken on an intention-to-treat basis, including all participants randomised, regardless of intervention received. The effectiveness of the trial interventions will be established by a change on the PHQ-9-A between baseline and 6-weeks post-baseline (primary endpoint) and 4-month follow-up (secondary endpoint), based on the interaction between time and condition, using mixed-effects linear modelling with an unadjusted p value of 0.05. Effect sizes will be calculated based on differences in change scores between baseline and 6-weeks post-baseline, using standard deviations of the change scores pooled across conditions. This modelling will account for all available data, under the missing at random assumption. However, attrition analyses will be conducted to determine whether missing data is associated with any baseline demographics (age, gender), mental health status (symptom severity) or other descriptive variables. Any baseline variables identified as substantially imbalanced between groups will be added to the models on an exploratory basis to confirm the robustness of the findings to this imbalance. Where distributional assumptions cannot be satisfied, other modelling may be used to confirm the robustness of the findings. Similar models will be used for secondary outcomes. To analyse the effects of adherence on outcomes, the mixed-effects repeated measures linear modelling will be repeated using the categorical adherence measure as a between group factor (adheres v non-adheres v control). These results will be published in the primary outcomes paper. Exploratory analyses will examine evidence for moderation, that is, whether the intervention was more effective for certain subgroups of the sample. Further, exploratory analyses will also examine evidence for mediation, that is whether the effects of the intervention were driven by other variables.

An additional file with free response data, matched with participant ID codes will be stored on UNSW OneDrive for qualitative analyses by the Chief Investigators, Trial Manager, and Research Officers/Assistants. Free-response questions will be analysed using thematic analysis to identify patterns across the responses. An inductive approach will be used to identify and group themes. The first stage of analysis will commence with familiarisation of the dataset by one researcher. Open coding will be used to summarise the data and create preliminary labels. Next, initial codes will be generated, and a coding framework will be created. A second researcher will then refine the codes and determine the final coding framework. Both researchers will recode the data using the finalised coding framework. An independent third researcher will review the data and themes to consolidate the findings. To support the validity of the analysis, analyst triangulation will be used whereby higher-order codes and final themes were determined by consensus among the researchers. The researchers coding the data will be instructed to regularly reflected on their personal reactions to ensure that they do not contaminate the data. The final themes will be presented in a separate paper on young people's perceptions of the interventions.

For participants allocated to trial arm 1 and 2, the study will also collect research data associated with their use of the intervention. This information will be used to determine which aspects of the intervention are important for improved outcomes. This trial will collect the following usage data from the *ClearlyMe* app: lessons completed, collections completed, features accessed, total time spent in app, content liked/disliked, content saved, and individual responses to lesson activities. This data will be extracted automatically from individuals' smartphones and transferred via the Internet to the Black Dog Institute Research Engine. This data will then be available for download (similar to the study assessment data) via the Black Dog Research Engine, connected to participants' study assessments using their unique participant identification code. Participants responses will be analysed to determine their compliance and engagement with the content, including linguistic analysis of their free responses. For participants allocated to trial arm 3 (i.e., the control condition), the study will also collect research data on the number of times each participant accesses each psychoeducation flyer via the URLs in the weekly SMSs. The time and date of access will be included.

For the risk management protocol, a report will be generated from the Black Dog Institute Research Engine that contains only participants' contact details (mobile phone number, email), name and age. This file will be password protected, stored on the UNSW OneDrive and only accessible by the Trial Manager, for conduct of any of the risk management telephone calls that are required during the study.

For participants allocated to Trial Arm 2, a report will be generated from the Black Dog Institute Research Engine that contains their mobile phone number, name and age. This file will be used to conduct the weekly SMS chats. This file will be password protected, stored on the UNSW OneDrive and only accessible to the research team members conducting the weekly SMS chats.

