H1= Participants who receive *ClearlyMe* (both self-directed and guided use) will report greater reductions in depressive symptoms between baseline and primary endpoint as well as baseline and secondary endpoint when compared to participants in the control condition;

H2= Participants who receive *ClearlyMe* (both self-directed and guided use) will report greater improvements in secondary outcomes (anxiety, psychological distress, emotional wellbeing,

quality of life, rumination, emotion regulation and CBT skill acquisition) between baseline and primary endpoint as well as baseline and secondary endpoint when compared to participants in the control condition;

H3= Participants' engagement with and completion of *ClearlyMe* will be significantly higher among participants who receive guided support when compared to participants who receive self-directed use.

Other exploratory hypotheses:

H4= Improvements in depressive symptoms among users of *ClearlyMe* will be moderated by gender, age, history of mental health, symptom severity at baseline, greater perceived need for care and higher levels of openness to digital mental health.

H5= Improvements in depressive symptoms among users of *ClearlyMe* will be mediated by rumination, emotion regulation, CBT skill acquisition, digital therapeutic alliance, and rates of engagement/completion.

5. Background Information

Adolescence is a significant and sensitive stage of life, whereby individuals evolve physically, socially, and psychologically as they transition to adulthood (Dahl et al., 2018). Given the rapid changes in a young person's development, this period also presents important risks and opportunities for young people's mental well-being. For example, a young person's access to a supportive environment, ability to maintain healthy sleeping and exercise behaviours, learn and develop coping, problem solving, emotional and interpersonal skills can influence their mental health (WHO., 2020). Poor mental health can have detrimental consequences to a young person's quality of life and their ability to function socially and academically (McGorry et al., 2011; Patel et al., 2007). Recent research suggests the global prevalence of depressive and anxiety symptoms in children and adolescents during the COVID-19 pandemic has increased, with 1 in 4 experiencing elevated depressive symptoms and 1 in 5 experiencing elevated anxiety symptoms, highlighting the need for mental health care (Racine et al., 2021).

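### The adherence analysis sets self-selected adherers and non-adherers against the undivided control arm and reports it with the primary results, without a non-randomised or exploratory label

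*Protocol*

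**What the plan says.** The analysis text is in Protocol section 10 (Treatment of Subjects).

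- **Primary analysis.** "Analyses will be undertaken on an intention-to-treat basis, including all participants randomised, regardless of intervention received". Effectiveness is judged by the time-by-condition interaction in a mixed-effects linear model of the PHQ-A.
- **Adherence analysis.** "To analyse the effects of adherence on outcomes, the mixed-effects repeated measures linear modelling will be repeated". The grouping factor has three levels, as the model is "repeated using the categorical adherence measure as a between group factor (adheres v non-adheres v control").
- **Where it is reported.** The next sentence is "These results will be published in the primary outcomes paper". It may cover more than the adherence results, but it includes them on either reading.
- **Labels.** The word exploratory comes only afterwards, for moderation ("Exploratory analyses will examine evidence for moderation, that is, whether the intervention was more effective for certain subgroups of the sample") and for mediation. No caveat, adjustment or causal method is attached to the adherence contrasts.
- **Use in the control arm.** Section 10 also records "research data on the number of times each participant accesses each psychoeducation flyer", with time and date. The adherence factor nevertheless leaves control as one group.
- **Expected arm differences.** H3 in section 4 states that engagement and completion "will be significantly higher among participants who receive guided support when compared to participants who receive self-directed use". Section 8 assumes d = 0.65 for guided and 0.35 for self-directed CBT.

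**The concern.** Two of the three groups are defined by what participants do after randomisation. The third is a randomised arm left whole, so it holds people who would have adhered to the app and people who would not. If the tendency to keep using the app is related to how depressive symptoms would have changed anyway, adherers v control mixes any app effect with that difference in prognosis. So does non-adherers v control.

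A second problem does not depend on prognosis. The factor has no term for app arm. If guided users adhere more, as H3 expects, and guidance works better, as section 8 assumes, then adherers contain more guided users, and the arm difference is read as an adherence effect.

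At stake is a statement in the main paper that the app works for those who use it. Selection or arm mix alone could produce that statement, tested with the same model as the randomised result and printed beside it. The protocol itself fixes the grouping, comparator, model, purpose and place of publication, so this is not detail left to a later analysis plan.

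**Working it through.** **Completers per arm.** A two-sided t-test at alpha 0.05 (sidedness assumed) with power 0.80 and d = 0.35 needs 129.1, so 130 per arm. Then 130/0.8 = 162.5, so 163 per arm and 3 x 163 = 489, the figure in section 8. It is used here only to set group sizes: 130 control completers and 2 x 130 = 260 app completers.

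**Selection, with no true effect in either app arm.** Let *p* be the adherent share and *g* the gap in SD between the change adherers and non-adherers would have shown anyway. Neither is in the protocol; both are assumed. The app arms as a whole match control, so

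- adherers minus control = (1 - p) x g
- non-adherers minus control = -p x g
- standard error for adherers v control = sqrt(1/(260p) + 1/130)

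Example: p = 0.4 and g = 0.3 give 0.6 x 0.3 = 0.18 SD. There are 104 adherers, the standard error is sqrt(1/104 + 1/130) = 0.132, and 0.18/0.132 = 1.37. A t-test with that non-centrality rejects 27.6% of the time.

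| p | g | Adherers v control (SD) | Non-adherers v control (SD) | Rejection, adherers v control |
|---|---|---|---|---|
| any | 0 | 0 | 0 | 5% |
| 0.3 | 0.2 | 0.14 | -0.06 | 16.3% |
| 0.3 | 0.4 | 0.28 | -0.12 | 49.4% |
| 0.4 | 0.3 | 0.18 | -0.12 | 27.6% |
| 0.6 | 0.2 | 0.08 | -0.12 | 10.3% |
| 0.6 | 0.4 | 0.16 | -0.24 | 26.9% |

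Positive means greater improvement. A negative *g* reverses every sign and leaves the rejection rates unchanged.

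**Check with a different model.** Here an adherence propensity is correlated with the change score (0.1 to 0.3, assumed), 30-70% adhere, there is no true effect, and 4,000 trials are simulated per scenario. Adherers differ from control by 0.05-0.35 SD. Their false-positive rate is about 7-13% at correlation 0.1, 14-37% at 0.2 and 26-70% at 0.3. Intention-to-treat on the same data stays at about 5%. At correlation 0 the adherence contrast also stays near 5%.

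**Arm mix, with no effect of adherence.** This takes the effect sizes in section 8, equal arms and assumed adherence rates.

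- 60% of guided and 40% of self-directed users adhere: adherers average (0.6 x 0.65 + 0.4 x 0.35)/1.0 = 0.53; non-adherers average (0.4 x 0.65 + 0.6 x 0.35)/1.0 = 0.47.
- 70% and 30%: 0.56 and 0.44.
- 50% in both: 0.50 and 0.50.

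A difference of 0.06 to 0.12 between adherers and non-adherers arises from arm alone.

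**The case against.** The strongest reply is that this is an added analysis. Effectiveness is established by the intention-to-treat model, and no hypothesis from H1 to H5 is tested by comparing adherers with control. That stands. A reader might infer that the trial's main result is biased; the documents do not support this, because the primary analysis keeps all randomised participants in their arms.

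Second, the size and sign of any bias are not known. The adherence rates and the prognostic gap above are assumptions, and a zero gap gives no selection bias. It is tempting to say that adherers will look too good. But section 10.1 describes ClearlyMe as non-sequential and used according to preference, so adolescents who improve early may stop, which could reverse the direction. This also stands, and the figures are illustrations only. The arm-mix problem remains even with a zero gap, provided adherence and effect both differ by arm.

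Third, merging of the two app arms is inferred from the three factor levels rather than stated as a rule. That is fair, but the listed levels leave no place for arm.

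Two further readings go too far. One is that use is observed only in the ClearlyMe arms: flyer access is recorded in control, although the factor does not use it. The other is to express the bias as a share of a planned difference of 0.25. The protocol states no such figure; 0.35 - 0.10 = 0.25 is an inference for the self-directed arm alone, and 489 reproduces from 0.35.

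**Conclusion.** The point holds as a flaw in a stated supporting analysis that should be corrected. The adherence contrasts are not randomised comparisons, yet they are described as effects of adherence, fitted with the primary model and reported with the primary results, without the exploratory label given to moderation and mediation.

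Confidence is high in the design flaw and low in any particular size or direction. The range of 0.08-0.28 SD and 10-49% false positives rests on no true effect, 260 app and 130 control completers, 30-60% adherent, and an assumed gap of 0.2-0.4 SD in favour of adherers. The arm-mix difference of 0.06-0.12 rests on the effect sizes in section 8 and assumed adherence of 60% v 40% to 70% v 30%. The intention-to-treat conclusion does not change.

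**What to change.** **Main change, in section 10.** State that the adherer and non-adherer results are exploratory and non-randomised. Report them descriptively and separately for the self-directed and guided arms, with no p-values against control. This needs no new assumptions.

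**If a causal adherence effect is wanted.** Estimate a complier average causal effect against control, with randomised allocation as the instrument and baseline PHQ-A as covariate, first for the self-directed arm. Handle missing 6-week scores under the same missing-at-random assumption as the primary model; two-stage least squares on observed scores alone would drop participants, and section 8 plans for 20% attrition. State the assumptions:

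- No effect of app use below the adherence threshold.
- No app access in the control arm. This must be confirmed. Section 9.3 says the app "will be released on the Apple and Google Play stores (for approved study participants to use only"), but control participants are study participants too, and the text does not restrict access by arm.
- If applied to the guided arm, no effect of the SMS coaching except through app use. This is doubtful, because section 10.1 provides weekly chats that include motivational coaching.

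**Cost.** A wording change and, if the causal estimate is added, one extra model with a wider interval. Data collection and sample size do not change. If the change counts as a deviation from the original statistical plan, Appendix J requires it to go to the ethics committee for approval before it is implemented.
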